### **6.2 Power calculation**

The number in each group is calculated to N=50 based on the results of Guimaraes et al. The AHI was used in the calculation.

Independent samples t-test, two-sided, anticipated effect size (Cohen's d) 0.8 (high), power  $\geq 80\%$ , probability level 5%. This gives a minimal sample size of 26 per group. The expected drop out of patients during the OMTa trial is 25% corresponding to a total of 20 patients. To accommodate for this potential dropout and to have adequate power for subpopulation analysis for gender, the sample size was increased to 100 (50 in each group).

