## **Outcomes**

The primary end point of the RCT is change in the AHI

Secondary endpoints:

1. Change in the Epworth Sleepiness scale and PROMs in the European Sleep Questionnaire.
2. OMTa adherence
3. Change in other conventional OSA severity indices (oxygen desaturation index, time below 90% saturation, nadir saturation) and change in novel OSA parameters in SAS identified in the development phase of the project.
4. Change in objective and subjective sleep quality (PSG and sleep diary, respectively).
5. Change in physiological parameters assessed by wearables.
6. Change in objective daytime functioning testing (PVT and Stroop test).
7. Change in self-reported self-efficacy as assessed by the PAM.
8. Changes in the Orofacial Myofunctional Evaluation with Scores (OMES).
9. Changes in the IOPI strength and endurance
10. Changes in hyoid position as assessed by a lateral cephalogram
11. Prediction of improvement in SDB severity by objective parameters from a 2D cephalogram obtained at baseline.

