### **6.1 Statistical analysis**

The Kruskal-Wallis test will be used for intergroup comparisons at each time point (T1 and T2). Intragroup comparisons will be performed by the Friedman test.

Inter-examiner agreement of OMT measurements will be determined by intraclass correlation coefficients (ICCs) and weighted kappa coefficient (Kw'). Effect sizes for statistically significant differences between T1 and T2 will be calculated using the Cohen's d statistic.

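### The power in section 6.2 is for a t-test at d = 0.8, but section 6.1 plans only Kruskal-Wallis at each time point and no between-arm test of change in AHI, so the stated power does not belong to the planned analysis

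*Combined protocol and SAP*

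**What the plan says.** Three parts of the combined protocol and SAP bear on the primary comparison.

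- **Outcomes:** "The primary end point of the RCT is change in the AHI".
- **Section 6.1, Statistical analysis:** "The Kruskal-Wallis test will be used for intergroup comparisons at each time point (T1 and T2". Within arms, "Intragroup comparisons will be performed by the Friedman test". No other test of a treatment effect is named.
- **Section 6.2, Power calculation:** "Independent samples t-test, two-sided, anticipated effect size (Cohen's d) 0.8 (high", with power of at least 80% at the 5% level, and then "This gives a minimal sample size of 26 per group". On the variable it says only "The AHI was used in the calculation", without a mean, an SD, or a statement of whether change or level is meant. The size is then raised to 50 per group to allow for 25% dropout and for subgroup analysis by gender.

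T1 and T2 are not defined. I read them as baseline and the 90-day outcome evaluation, the only assessments the protocol schedules in the randomised period.

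**The concern.** A power statement is useful only if it describes the test that will be run on the quantity that will be tested. Here three descriptions differ. The endpoint is a change, the planned between-arm test is a rank test at each visit, and the powered test is a t-test on an unspecified form of AHI.

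The T1 comparison concerns the arms before treatment, so only the T2 comparison can show an effect between arms. It uses no baseline information and is not a test of change. The Friedman test looks within each arm and cannot replace a between-arm comparison.

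At stake is whether the stated 80% applies to anything the trial will do, and whether the choice between change and level, or between t-test and ranks, stays open until results are known.

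**Working it through.** **Inputs from the plan.** Two-sided 5%, d = 0.8, power at least 80%, 26 per group (section 6.2); 1:1 allocation (Randomization); 50 per group and 25% dropout (section 6.2). Expected completers: 50 × 0.75 = 37.5, taken as 37 per arm.

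**Assumptions not in the plan.** Normal data unless stated; equal SDs at T1 and T2; T1–T2 correlation rho, shown from 0.3 to 0.8.

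**Step 1: reproduce the plan's figure.** Noncentral-t power for two independent groups at d = 0.8 solves to n = 25.52, hence 26 per group. Power is 79.1% at 25 and 80.7% at 26. The plan's 26 is confirmed.

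**Step 2: same d, planned test.** With two arms, Kruskal-Wallis is equivalent to the two-sided rank-sum test. With N = 2n and arm rank sums R₁ and R₂:

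H = 12/(N(N+1)) × (R₁²/n + R₂²/n) − 3(N+1), compared with chi-square on 1 df.

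Simulated power under normality, 100,000 or more runs per row, with the t-test beside it:

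| n per arm | t-test | Kruskal-Wallis |
|---|---|---|
| 26 | 80.7% | 78–79% |
| 27 | 82.2% | 80.4% |
| 37 | 92.4% | 91% |
| 50 | 97.7% | 97% |

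The asymptotic relative efficiency of 0.955 agrees: 25.52 / 0.955 = 26.7, so 27 per group.

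**Step 3: shape of the distribution.** For a pure shift of 0.8 SD at 26 per group, with assumed shapes, Kruskal-Wallis has about 75% (uniform), 87% (t with 5 df) and 89% (gamma with shape 2). The effect of using ranks can go either way.

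**Step 4: change or level.** Let σ be the SD at each visit. The SD of change is σ√(2(1−rho)). If d = 0.8 describes change, the expected between-arm difference in change is 0.8 × σ√(2(1−rho)). Randomisation makes the expected baseline difference zero, so this is also the expected difference at T2. Dividing by σ:

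d at T2 = 0.8 × √(2(1−rho))

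For example, at rho = 0.7 it is 0.8 × √0.6 = 0.62. Kruskal-Wallis power on T2 values at 37 per arm:

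| rho | d at T2 | Power |
|---|---|---|
| 0.3 | 0.95 | 97–98% |
| 0.4 | 0.88 | 95% |
| 0.5 | 0.80 | 91% |
| 0.6 | 0.72 | 84% |
| 0.65 | 0.67 | 79% |
| 0.7 | 0.62 | 73% |
| 0.8 | 0.51 | 55% |

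Power drops below 80% from a rho of about 0.65. With no dropout (50 per arm) it is about 85% at 0.7 and 68% to 69% at 0.8.

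**Step 5: the comparison that section 6.2 describes.** If d = 0.8 is for change and change is compared by a t-test, power at 37 per arm is 92.4%, whatever rho is.

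**The case against.** The strongest reply is that nothing of consequence has gone wrong. The 26 is correct for the test named with it. A t-test formula is a common stand-in for a rank test, the difference is one patient per group, and the trial enrols 50 per group. With 37 completers the rank test still has about 91% if d = 0.8 describes T2 values. A rank test is usually chosen because normality is doubted, and with a skewed AHI it may do better than the t-test. All of this stands.

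The change-versus-level loss is also conditional. It needs d = 0.8 to mean change, equal SDs, and rho of about 0.65 or more. At rho of 0.5 or less, testing T2 values costs nothing beyond the small loss from ranks and may gain. The documents give no rho. Entry is limited to a respiratory event index below 30, which tends to lower it; three recorded nights per assessment, if averaged, would raise it. Neither settles the value.

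A reader might infer that section 6.2 contains a miscalculation, or that the trial is underpowered. The documents support neither. The first is refuted by reproducing the figure, and the second depends on facts the plan does not state.

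The reply does not remove the mismatch. Section 6.1 contains no between-arm test of the stated primary endpoint, and section 6.2 leaves open which quantity it powers. Nor is the increase to 50 per group free reserve, since section 6.2 assigns part of it to gender subgroups.

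**Conclusion.** The point holds as an inconsistency between sections 6.1, 6.2 and Outcomes, and it should be corrected. The stated power is right for a t-test that the plan does not include.

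- **Rank test alone:** minor. It costs about 2 percentage points at 26 per group under normality, is covered by the planned enrolment, and may reverse with skewed data.
- **Unstated meaning of d = 0.8:** the part that could matter. At 37 completers per arm, power on T2 values is about 91% if d describes T2. If d describes change, it runs from 97–98% down to 55% over rho 0.3 to 0.8, and is below 80% only from about 0.65.

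The second result rests on normality, equal SDs at both visits and an assumed rho. It shows that the plan's power is undetermined, not that it is inadequate.

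**What to change.** **Section 6.1:** name one primary between-arm comparison of change in AHI, of the t-test type that section 6.2 powers. Kruskal-Wallis at each visit can stay as supportive.

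**Section 6.2:** state that d = 0.8 refers to that quantity, and give power at the expected completers (about 92% at 37 per arm if d = 0.8 is for change). If d = 0.8 was meant for AHI at T2, say so and give a separate effect size for change.

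**If Kruskal-Wallis on T2 values is kept as the primary test:** restate the minimal size and power for it (27 per group under normality, with d defined on T2 values) and show the range over rho if d came from change scores. The Outcomes section would then need to agree with what is tested.

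**Cost:** with the first route, wording and routine analysis, with no extra patients or measurements. Keeping the T2 test could bring a real shortfall into view if d describes change and rho is high. Either way, settle it before any outcome data are compared by arm, so that the primary test is not chosen afterwards.

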### **Baseline evaluation**

Eligible candidates completing auto-monitoring less than 70% of the days prior to baseline assessment will be excluded (see exclusion criteria above). Questions related to the “Sleep Well” application will be answered. [name] and [name] respectively will also ensure that at least 40 of 100 participants are female. After final inclusion, [name] and [name] respectively will schedule the sleep registration and an outcome evaluation session 90 days later. All data collected during the baseline evaluation will be collected in the “Redcap” case report form (CRF).

Further, clinical evaluation will consist of height, weight, standardized blood pressure and a breath holding test. Digital oral scanning will be obtained at both sites. Thereafter, the quantitative scores (OMES) for assessing the myofunctional therapy will be performed and video filmed with one front camera and one camera with a 45-degree angle on the face. The purpose of the video filming is inter rater reliability analyses. All participants will be placed in a chair without arm- or backrest. Body posture on the chair will not be corrected. The baseline assessment will last approximately 90 minutes.

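### A sample of 100 cannot give 80% power within each sex under the plan's own assumptions, and 20 patients is not 25% of any total the plan states

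*Combined protocol and SAP*

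**What the plan says.** Section 6.2 (Power calculation) bases the sample size on AHI. The test is "Independent samples t-test, two-sided", with "anticipated effect size (Cohen's d) 0.8 (high"), at least 80% power and a 5% level. The result is stated as "This gives a minimal sample size of 26 per group".

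On dropout, the section says: "The expected drop out of patients during the OMTa trial is 25% corresponding to a total of 20 patients". It then gives two reasons for going beyond 52: to cover that dropout and "to have adequate power for subpopulation analysis for gender, the sample size was increased to 100 (50 in each group"). It shows no subgroup effect size, subgroup number or subgroup power.

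The sex mix is set elsewhere. Under Baseline evaluation, staff are to "ensure that at least 40 of 100 participants are female". The Randomization section gives 1:1 allocation, done separately by sex, and refers to a 40/60 gender balance. Section 6.1 (Statistical analysis) describes no analysis by gender, neither a test within each sex nor an interaction.

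**The concern.** A comparison within one sex, at the same effect size, significance level and power, needs as many people per arm as the whole trial was calculated to need. Doubling 52 to about 100 could therefore serve two subgroups only if the sexes were almost equal in number and nobody dropped out. The plan expects neither.

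Dropout alone takes 52 to about 70. The remaining 30 or so participants rest on the gender argument, so if it fails, the stated reason for much of the sample size fails with it.

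Readers told in advance that subgroup power was adequate may take a null result in women as evidence of no effect in women. They may also take a significant result in men only as a real sex difference.

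**Working it through.** **Inputs.** From section 6.2: two-sided independent-samples t-test, d = 0.8, 5% level, power at least 80%, 26 per group, 25% dropout given as 20 patients, 100 randomised. From Baseline evaluation and Randomization: at least 40 women of 100, a 40/60 balance, 1:1 allocation. Assumptions added here, because the plan gives none: the same d applies in each sex, and dropout is equal by sex and arm.

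**The plan's own figure.** For n per arm, power comes from the noncentral t distribution with 2n − 2 degrees of freedom and noncentrality d × √(n/2). Solving for 80% gives n = 25.52, rounded up to 26, where power is 80.7%. The plan's 26 is reproduced.

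**Completers needed for both sexes.** 26 per arm × 2 arms × 2 sexes = 104. The trial enrols 100, so no sex split gives 80% in both sexes, even with no dropout.

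**Power within each sex.** n per arm = 50 × share of that sex × (1 − dropout), with d = 0.8.

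| Case | Women: n per arm | Women: power | Men: n per arm | Men: power |
|---|---|---|---|---|
| 40/60, no dropout | 20 | 69% | 30 | 86% |
| 40/60, 20 of 100 drop out | 16 | 59% | 24 | 77% |
| 40/60, 25% drop out | 15 | 56% | 22.5 | 75% |
| 50/50, no dropout | 25 | 79% | 25 | 79% |
| 50/50, 25% drop out | 18.75 | 66% | 18.75 | 66% |

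With whole numbers of men, 22 per arm gives 74% and 23 gives 76%. The smallest effect detectable with 80% power after 25% dropout at 40/60 is d = 1.06 in women and 0.85 in men.

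**If the gender analysis is an interaction.** The standard error of the difference between the two sex-specific effects, in SD units, is √(2/15 + 2/22.5) = 0.471. If the effects differ by 0.8 SD, power is 39% after dropout and 49% without it. If they differ by 0.4 SD, power after dropout is 13%.

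**Chance of a misleading pattern.** If the true effect is d = 0.8 in both sexes, the probability that men are significant and women are not is 0.746 × (1 − 0.562) = 0.33 after dropout.

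**What 80% in women would take at 40% female.** 52 completing women / 0.75 / 0.4 = 173.3, so about 174. Rounding up to 35 enrolled women per arm gives 70 / 0.4 = 175.

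**The dropout count.**
- 25% of 52 = 13.
- 52 / 0.75 = 69.3, so 70 randomised, which is 18 extra.
- 25% of 100 = 25.
- 20 / 0.25 = 80, a total stated nowhere.

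**The main comparison.** 100 × 0.75 = 75 completers, 37 to 38 per arm. Power at d = 0.8 is 92% to 93%, and 80% power is reached at d of about 0.66.

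**The case against.** The best case for the plan has four parts.

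1. **The subgroup target is not defined.** The plan ties d = 0.8 and 80% to the overall comparison and never says what counts as adequate for a subgroup. Carrying those values into each sex is an assumption. That is so, but the plan offers no other values, and a larger effect would have to rescue the claim: d = 1.06 in women after dropout, when section 6.2 already calls 0.8 high.

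2. **Forty women is a minimum.** With 50 women and no dropout, power is 79%, practically on target. But the plan itself expects 25% dropout, and an equal split then gives 66% in each sex. The figures of 56% and 75% should be labelled as applying at the 40% minimum.

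3. **The 20 may have an innocent origin.** 80 × 1.25 = 100 is a common inflation shortcut. That may explain the number but does not make it right, since 20 of 100 is 20%. The choice does not change the conclusion: with 20 dropouts, power is 59% in women and 77% in men.

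4. **The main result is untouched.** No gender endpoint or gender test is specified, so the error is confined to section 6.2. This is correct and limits the consequences. It does not make the stated justification true, and with no specified gender analysis nothing else in the plan guards against misreading one.

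**Conclusion.** The concern holds. At the plan's own effect size, significance level and power target, 100 participants do not give adequate power by gender under any sex split. At the 40% female minimum with 25% dropout, power is about 56% in women and 75% in men, and it falls short in both sexes whether 20 or 25 participants drop out. Separately, 25% and 20 patients do not agree for any total in the plan.

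These figures assume the same standardised effect in each sex and equal dropout by sex and arm. They are for the t-test used in section 6.2. Section 6.1 plans a Kruskal-Wallis test, which would have slightly less power with normal data (about 54% in women, assuming a relative efficiency of 0.955). The 26 per group is correct, and the overall comparison keeps 92% to 93% power at d = 0.8.

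**What to change.** Rewrite the sample-size paragraph in section 6.2 as follows:

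- 26 completers per arm (52) are needed; allowing for 25% dropout gives 70 randomised.
- 100 randomised leaves about 75 evaluable (37 to 38 per arm), with 92% to 93% power at d = 0.8 and 80% power at d of about 0.66.
- Replace the 20 patients with 25 of 100. If the sponsor in fact expects 20 dropouts of 100, the rate should read 20% and the figures above should be recalculated.
- Delete the claim of adequate power by gender. State instead that power within sex at d = 0.8 is about 56% for women and 75% for men, at the 40% female minimum and with dropout equal by sex and arm.

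In section 6.1, add that gender will be examined as an exploratory arm-by-sex interaction, reporting the effect in each sex and their difference with 95% confidence intervals, and that separate significance tests in each sex will not be used to claim a sex difference.

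The cost is wording only. Recruitment, the sex quota and the procedures stay as they are. The subgroup statement becomes less favourable, and the overall power can be stated as higher than the plan now shows.

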## **7 Costs/finance**

Horizon 2020, grant number 965417

## **8 Ethical aspects**

### ***Study management, study monitoring, data and sample management***

The study site will have a designated study coordinator and ethical guardian who will be appropriately trained and informed about the nature of the study, ethical and data security aspects; including informed consent, good clinical practice (GCP) and applicable regulatory requirements.

All clinical patient source data will be stored at the hospital according to clinical routines. The project leader will be responsible for the “code key” with which it is possible to connect the data to the patient and this data will be kept offline.

### ***Regulatory / ethics status***

The following directives will be applied: Good Clinical Practice (GCP) rules according to the declaration of Helsinki.

The ASAP Clinical Cohort has appointed a user representative from the Association for Sleep Disorders in Norway. The same representative will be invited to provide end user feedback in this study.

## **9 Spread of results, international collaboration and end of project**

Results will be published in international, peer reviewed medical journals in accordance with the international committee of medical journal editors (ICMJE) criteria, <https://www.icmje.org/>. The international collaborators, [name] and [name] are involved in training and supervision of the PhD student respectively. They will be involved in data analysis inside the Tjenester for Sensitive Data (TSD) platform. The project will end on February 28th 2025, data will be stored for an additional 5 years.

# 10 Appendix

## 1 Paper version of sleep diary

### SOVNDAGBOK

Navn: \_\_\_\_\_ Spørsmål 1 til 4 fylles ut for sengetid, resten av skjemaet fylles ut om morgenen. Husk å notere dato.

Dato:	Eksempel 30.08.19	Mandag	Tirsdag	Onsdag	Torsdag	Fredag	Lørdag	Søndag
1. Hvordan har du fungert i løpet av dagen? 1 = veldig bra, 2 = bra, 3 = verken bra eller dårlig, 4 = dårlig, 5 = veldig dårlig	4							
2. Aktive mestringsstrategier for dårlig dagfunksjon :								
a. Antall minutter korte lurer/hvile med lukkede øyne	10 min							
b. Ca antall gjesp i løpet av våkentiden	10							
c. Minutter bevegelse for å aktivere våkenhetssystemet	2							
3. Har du tatt sovemedisin og/eller alkohol som hjelp til å sove ? Notér medikament, samt evt alkoholinntak	1 Imovane 1 glass rødvin							
4. Når gikk du til sengs? Når skrudde du av lyset?	22.30 23.00							
5. Hvor lang tid tror du det tok å sovne?	45 min							
6. Hvor mange ganger våknet du i løpet av natten?	3							
7. Hvor lang tid tror du at du totalt var våken i løpet av natten?	30 min							
8. Når våknet du opp om morgenen uten å få sove igjen? Notér tidspunktet for din endelige oppvåkning.	06.15							
9. Når stod du opp?	06.40							
10. Hvordan vurderer du nattens søvn? 1 = veldig lett, 2 = lett, 3 = middels, 4 = dyp, 5 = veldig dyp.	1							

